5.4.3 Primary Outcomes – Main Study

Food Intake (24-Hour Dietary Recalls): Food intake (secondary outcome) will be assessed via 6 telephone-administered, 24-hour dietary recalls on days 1-3 and 29-31. A trained member of the research staff will use a multi-pass method with an interactive computerized software program, the ASA24® (Automated Self-Administered 24-hour Recall), to determine total kcal/day (outcome variable). The ASA24® was created by investigators at the NCI. Three recalls are considered optimal for assessing dietary intake, especially when weekend and weekdays are assessed, as we propose to do when possible. If participants are unable to complete a scheduled recall over the telephone or are onsite for a scheduled visit, participants may be asked to complete a 24-hour dietary recall with the research staff in-Center. Comparable accuracy can be achieved when administered in-person and over the telephone. Food recalls are widely used, reliable, and valid, assessing kcals/day within 10% of actual dietary intake measured under laboratory observation and by doubly labeled water.

fMRI Tasks: See section 5.2.8: fMRI Scanning Visits for the complete descriptions of the in-scanner tasks.

Food Cue-Induced Craving. The key outcome for this variable is BOLD signal change for most appetizing foods (versus water, and versus least appetizing foods as an active control). Primary regions of interest for the BOLD fMRI analysis are insula, caudate, OFC and ACC. As a secondary measure, food craving will be assessed prior to and after completion of the scan. The food craving assessment is the 3-item "desire" subscale of the reliable and valid state version of the Food Craving Questionnaire (FCQ-S).

Relative Reinforcing Value of Food (via Food Reward Reinforcement/Choice task). The primary behavioral outcome will be the amount of additional effort subjects are willing to

CONFIDENTIAL

This material is the property of the University of Pennsylvania. Do not disclose or use except as authorized in writing by the study sponsor

expend in order to obtain food. The primary regions of interest for the BOLD fMRI analysis are VS and vmPFC. Within these regions, the food choices (all 50 trials where food is an option) vs. fixation will be the primary contrast. Selection of this primary contrast will ensure the same stimuli will be analyzed across participants and conditions and maximize statistical power for detecting food-related activation.

Working Memory N-Back Task. Based on our prior work, the primary performance measure will be correct reaction time, and the secondary measure will be number correct; the primary regions of interest for the BOLD analysis will be DLPFC and medial/frontal cingulate gyrus.

Primary Outcomes (Recruitment & Retention Pilot Study):

Meeting Eligibility Criteria: The primary outcome is the percentage of subjects who meet final eligibility criteria (i.e., enrollment). We chose this as the outcome based on our data suggesting that subjects who meet these criteria are highly likely to reach ITT status.

Secondary Subjective Outcomes (Recruitment & Retention Pilot Study):

Impressions of Research: Attitudes towards research; motivations for participation; perceived risks/benefits of research; and perceptions of influence or coercion will be assessed via text survey at baseline (following phone screen), mid-way through participation and at study completion. All secondary outcomes will be delivered via the W2H platform and imported into REDCap. Study staff will attempt to contact subjects who withdraw or are lost-to-follow up to identify reasons for withdrawal. We will assess overall satisfaction with the study, acceptability of the frequency and content of messages (IP and IC groups only). For all models, a term will be included for individual study as well as other relevant covariates (e.g., sex, age, income).

5.4 Tissue Specimens

Urine: A urine sample will be required at the Intake Visit and both fMRI Scan Visits for drug (~30ml) and pregnancy screenings. These samples will be disposed of following the conclusion of the study visit.

5.5 Sample Size Determination

We plan to test hypotheses at a global 5% Type I error (alpha) for each family of hypotheses, and have chosen a completed sample (N=110) that will achieve at least 80% power using 2-sided tests. Our analysis of power was based on “effect size” (standardized difference). Effect sizes were calculated from our own preliminary data, from published data summaries, and from published estimates of effects (e.g., t statistics, coefficients, p-values) using validated summary methods. We have several hypotheses and more than one outcome measure for some (e.g., different brain regions). We will control error in a family-wise manner, adjusting alpha (Bonferroni Aims 1 and 2, Hochberg step-up procedure for Aim 3) for the number of tests within each hypothesis family. Bonferroni corrections will also be adjusted for the correlations among multiple outcomes.

Aim 1 includes 2 hypotheses (**H1a&b**) regarding treatment effects on neural responses, including 5 ROIs responding to food-related tasks. We test at $p<0.02$ because of the high correlation among ROIs within subjects ($\rho=0.54$). Estimates of effect size from our center data ($d=0.36$) indicate that we have 80% power to detect the effects. Aim 1 also tests hypothesis **H1c** for cessation effects. At the Bonferroni corrected threshold of $p=0.0167$, we have 80% power to detect small to medium effect sizes ($d=0.37$).

CONFIDENTIAL

This material is the property of the University of Pennsylvania. Do not disclose or use except as authorized in writing by the study sponsor

Aim 2 (H2a&b) essentially tests for mediation. The hypothesis that cessation increases food intake will be tested at 0.05, with power for effect sizes $\sim d=0.32$. For Aim 2b (ROIs predicting food intake), we expect a weaker correlation than H1a ($\rho=0.4$), and our adjusted threshold for significance is $p<0.01$. Expected effect sizes are approximately 0.5, and we expect 96% power to detect the effects.

Aim 3 begins with the model in Aim 2b above, and tests interacting effects of working memory-related BOLD signal and food reinforcement (or food cue reactivity) on food intake. We will reduce the complexity of this analysis by using difference scores (pre minus post) to model a 2-way interaction between working memory and food reinforcement on food intake. We will only test for brain ROIs found to be sensitive to treatment in Aim 1; the number of tests for interaction is uncertain. We anticipate that these effects will be positively correlated and will use the Hochberg step-up procedure, which is robust to correlations among outcomes in the range we expect. For purposes of power calculation, we assumed a correlation of 0.5, which resulted in a corrected p-value of 0.02 for 5 tests. Keeping the independent variables continuous, we can detect an interaction term (one-sample per subject, standardized) of $d=0.36$ with 80% power. Literature estimates for similar interactions were 0.65, 0.66, and 0.35. The lowest estimate gives 77% power, and the average (0.55) yields 98% power.

Recruitment & Retention Pilot Study:

Power is provided for our primary aim. The analysis will compare the enrollment rates between the four intervention arms, and examine main and interaction effects. For SR arm, we expect a 28% of subjects who schedule an intake will be eligible and enroll (based on existing data across the four studies). With the proposed sample of 576, we have $>80\%$ power ($\alpha=.05$) to detect a difference between the SR arm and the IP and CM arms of 12%, corresponding to an OR of 1.75. For the interaction term, we have 80% power ($\alpha=.05$) to detect a departure from additivity of the main effects corresponding to a ratio of odds ratios (ORR) of 5.5.

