2.1 Main Study

Aim 1: To test three putative brain mechanisms underlying increased caloric intake during nicotine withdrawal using an abstinence challenge paradigm (within-subject).

H1a: Brain signal will be associated with decreased working memory (WM) in the dorsolateral prefrontal cortex (DLPFC) and reduced suppression of activity in the posterior cingulate cortex (PCC).

H1b: There will be increased food cue-induced activity in the insula, anterior cingulate cortex (ACC), orbitofrontal cortex (OFC), and ventral striatum/nucleus accumbens (VS/NAC).

H1c: Increased food reinforcement choice-related activity in VS/NAC and ventromedial prefrontal cortex (vmPFC) will predict increased caloric intake (abstinence vs. smoking).

Aim 2: To evaluate the relative contribution of task-related brain signal (WM, Food Cue Response, Food Reinforcement/Choice) in prediction of nicotine abstinence-induced increase in caloric intake (within-subject).

H2a: Brain responses (H1a-c) will characterize abstinence challenge-induced change in caloric intake more accurately than clinical (age, sex, nicotine dependence, BMI), subjective (craving, withdrawal), and behavioral performance measures alone.

CONFIDENTIAL

This material is the property of the University of Pennsylvania. Do not disclose or use except as authorized in writing by the study sponsor

H2b: The relative contribution of domain-specific brain signal (WM, food cue reactivity and food reinforcement) to the prediction of abstinence challenge-induced increase in caloric intake will be evaluated (regression model).

EXPLORATORY AIM (between group): To provide a baseline comparison in food-related brain response between smokers and non-smokers.

This study will: (a) drive new insights about how the brain can constrain or promote the ability of smokers to prevent PCWG; and (b) lead to new theories and interventions that integrate neural and behavioral frameworks important for promoting behavior change. Support for our predictions would inform testing of novel approaches to prevent PCWG, such as computerized neurocognitive exercise training to increase DLPFC activity and shift activity away from reward sensitive brain networks.

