2.2 Overall Objectives - (Recruitment & Retention Pilot Study)

Aim 1: To evaluate the effects of information provision and incentives, alone and in combination, on study enrollment rates.

Hypothesis: Behavioral economic interventions will (Information provision & contingency management) will produce higher rates of enrollment compared to standard recruitment.

3 Study Design

General Design – Main Study

This is a within-subject cross-over neuroimaging investigation of 3 potential neural mechanisms of increased caloric intake during initial smoking cessation. Eighty smokers will be scanned on 2 occasions: (1) after 4 days of monitored abstinence (biochemically verified), and (2) after 4 days of smoking as usual (order counterbalanced) (**Figure 3**). In addition, 30 healthy non-smokers (matched for sex, age, and education) will complete one period of the study to serve as a baseline comparison group (see Exploratory Aim). As in prior studies, participants will have fasted overnight and be provided with a standard meal (BOOST® shake) when they arrive on testing days 4 and 32. Blood oxygen level dependent (BOLD) fMRI sessions will assess BOLD signal at rest and while performing tasks for food cue reactivity, food reinforcement (choice task), and working memory (N-back). Additional measures will be administered out of scanner (**Figure 3**). Caloric intake will be assessed on days 1-3 and 29-31 using a validated dietary recall procedure (days 4 and 32 are fMRI scan days and intake will be standardized). Caloric intake is the primary behavioral outcome. Task-induced BOLD signal change in hypothesized regions of interest and performance on the working memory, food cue, and food reinforcement tasks are the mechanistic variables.

CONFIDENTIAL

This material is the property of the University of Pennsylvania. Do not disclose or use except as authorized in writing by the study sponsor

Figure 3

Non-smoker Control Group (Baseline):

Day	-7	1 2 3 4
Activity	Intake	Period 1*

*non-smokers complete phase 1 with identical monitoring and assessment

**order of periods (abstinence vs smoking) is counter balanced

Smoker Group (within-subject):

Day	-7	1 2 3 4	5-28	29 30 31 32	1 Month Follow-up
Activity	Intake	Period 1	Washout	Period 2	Web-based Survey
State	Smoke	Abstain**	Smoke	Smoke	N/A

Behavioral Outcome:

- Caloric intake (dietary recall; Days 1-3* & Days 29-32)

Intermediate Outcomes: Day 4* & Day 32

- Food reward (out of scanner)
- Working memory (fMRI)

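### The plan names conflicting primary food-cue regions, and its 0.02 threshold for five food-task regions gives about 7.8% family-wise error, not the promised 5%, if they form one equally correlated family

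*Combined protocol and SAP*

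**What the plan says.** **Error control.** Section 5.5 states: "We plan to test hypotheses at a global 5% Type I error (alpha) for each family of hypotheses". Tests are two-sided. Aims 1 and 2 use Bonferroni, relaxed for correlation by a method that is not named. For H1a and H1b, "including 5 ROIs responding to food-related tasks", it continues: "We test at $p<0.02$ because of the high correlation among ROIs within subjects". The correlation is given as 0.54, and 80% power is claimed at d=0.36. H1c is set at 0.0167 and Aim 2b at 0.01. Aim 3 is to be tested by Hochberg, but its power calculation assumes 0.02 for five tests at correlation 0.5. Aim 3 takes forward only the regions that respond in Aim 1.

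**Food-cue regions.**

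| Place | Regions |
|---|---|
| Section 2.1, H1b | "There will be increased food cue-induced activity in the insula, anterior cingulate cortex (ACC), orbitofrontal cortex (OFC), and ventral striatum/nucleus accumbens (VS/NAC") |
| Section 5.4.3, food cue task | Primary: caudate, ACC, OFC, insula |
| Section 5.6, group-level analysis (cue and reinforcement tasks) | Primary: vmPFC, VS. Secondary: insula, OFC, amygdala, MF/CG |

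**What is tested.** Section 5.5 treats H1a and H1b as abstinence effects on neural response. Section 5.6 describes the Aim 1 test as a regression of the caloric-intake difference on the BOLD difference. Section 5.6 also lists both percent signal change and activation extent as measures for the key hypotheses, then names only mean percent signal change under its hypothesis-testing heading.

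**The concern.** A correlation of 0.54 does not obviously justify doubling the plain Bonferroni level for five tests from 0.05/5 = 0.01 to 0.02. If it does not, the plan's decision rule misses its own stated error rate.

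The conflicting lists matter more. They determine which results are confirmatory, and they also determine how many tests 0.02 has to cover. As written, both could be settled after the results are known.

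The effect also carries forward. Section 5.5 sends only Aim 1-positive regions into the Aim 3 interaction tests on caloric intake, so a false positive in Aim 1 becomes a candidate there.

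**Working it through.** **1. The plan's own power figure.** Noncentral t for a paired mean difference, two-sided 0.02, 80 smokers: noncentrality 0.36 × √80 = 3.22, critical value 2.374 (79 df), power 79.9%. The stated 80% is reproduced with 80 smokers; with N=110 it would be 92.0%. The power arithmetic is sound. The question is the threshold.

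**2. Family-wise error at 0.02.** Inputs from Section 5.5: m = 5, ρ = 0.54, two-sided 0.02, so c = 2.326. Assumptions: one family, equal correlations, and ρ applying to the abstinent-minus-smoking differences.

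FWER = 1 − ∫ φ(u) [Φ((c − √ρ·u)/√(1−ρ)) − Φ((−c − √ρ·u)/√(1−ρ))]^m du

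| Tests m (ρ = 0.54) | FWER |
|---|---|
| 2 | 3.7% |
| 3 | 5.2% |
| 4 | 6.5% |
| 5 | 7.8% |
| 6 | 8.9% |

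Simulated paired t-tests with n=80 also give 7.8% for five. Independence would give 1 − 0.98^5 = 9.6%. With equal correlations, 0.02 holds 5% for five tests only at ρ of about 0.85. At ρ = 0.54 the threshold that holds 5% is 0.0124 for five tests and 0.0150 for four.

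**3. Unequal correlations averaging 0.54.** Blocks of 3+2 regions have 4 within-block and 6 between-block pairs.
- 0.75 within, 0.40 between: (4×0.75 + 6×0.40)/10 = 0.54; FWER 7.3%.
- 0.90 within, 0.30 between: mean 0.54; FWER 6.2%.
- 0.99 within, 0.24 between: mean 0.54; FWER about 4.6%.

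A 4+1 split with 0.90 within and 0 between gives 5.9%. Of the patterns tried, only the near-duplicate 0.99 blocks fall below 5%.

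**4. Regression reading of Section 5.6.** With n=80 and 0.02, five separate regressions give 7.9%. One joint model gives 9.2% (correlation between coefficients −0.54/(1 + 3×0.54) = −0.206).

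**5. Where 0.02 may come from.** The Dubey/Armitage-Parmar formula gives 1 − 0.95^(1/5^0.46) = 0.0242, which rounds to 0.02. This is conjecture, since the plan names no formula. At 0.0242 the FWER would be 9.2%.

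**6. Other thresholds in Section 5.5.**
- H1c, 0.0167, three tests: 4.4% at ρ = 0.54 and 4.9% if independent. Not affected.
- Aim 2b, 0.01, ρ = 0.4: 4.5% if there are five tests (the count is not stated; six would give 5.2%).
- Aim 3, 0.02 for five tests at 0.5: 8.0% if it were used as a fixed threshold.

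**7. How many regions?** H1b and H1c in Section 2.1 together name five distinct regions (insula, ACC, OFC, VS/NAC, vmPFC). Section 5.4.3 names six over the two food tasks: four for cue, plus VS and vmPFC for reinforcement. Section 5.6 names two. The count of five in Section 5.5 therefore matches neither the outcomes section nor the methods section. The reinforcement regions do agree between 5.4.3 and 5.6. A smaller conflict of the same kind: H1a names the PCC, which is absent from the primary N-back lists in 5.4.3 and 5.6.

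**8. Power at a threshold that holds 5%.** At 0.0124 the critical value is 2.559 and power at d=0.36 is 74.4%; 80% needs d of about 0.38. Simulated Holm (n=80, ρ = 0.54) gives per-region power of 72% if one region responds and 81% if all five do.

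**The case against.** The strongest reply is that the family is not defined. Section 5.5 says that the tests include five food-task regions. It does not say that those five form one family, or that only five are tested. Its labels also differ from Section 2.1: H1c there predicts caloric intake, whereas 5.5 calls it a cessation effect, and Section 2.1 has no Aim 3. If families are formed by task and Section 5.6's two primary regions apply, 0.02 holds comfortably at 3.7%. This stands, and it makes 7.8% conditional. It does not rescue the plan, because that reading requires choosing 5.6 over 5.4.3, and the documents give no basis for the choice.

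Second, 0.02 might be only a planning figure, as it is for Aim 3, where Hochberg is the actual test. For Aim 1, however, the plan says that it tests at that level and names no other correlation-adjusted procedure.

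Third, 7.8% is above every unequal-correlation result tried with mean 0.54. That is fair. The excess over 5% is about 1 to 3 percentage points in the moderate cases.

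A reader might infer that the conclusion on caloric intake itself is undermined. The documents do not support that: "Caloric intake is the primary behavioral outcome", and Section 5.5 gives the cessation effect on intake its own test at 0.05. The opposite inference, that only BOLD tests are touched, also fails, because of the Aim 1 regression in Section 5.6 and the Aim 3 selection rule in Section 5.5.

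**Conclusion.** Both parts hold. Confidence differs between them.

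- **Conflicting primary food-cue lists: high confidence.** This is visible in current text, needs no modelling, and nothing elsewhere in the documents resolves it.
- **0.02 does not deliver 5%: moderate confidence in the exact figure.** It is about 7.8% for one family of five with equal correlations of 0.54, and about 6% to 7.3% under moderately unequal correlations with that mean. With equal correlations of 0.54, 0.02 is adequate for two regions but not for three or more.

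It would be too strong to say that the error rate is 7.8% whatever the structure, that it can reach 5% only at a correlation of 0.85 (true for equal correlations only), or that the multiplicity plan fails throughout. H1c is sound, and so is Aim 2b if it has five tests. This should be fixed before analysis. It does not invalidate the design.

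**What to change.** 1. Reconcile Sections 2.1, 5.4.3, 5.5 and 5.6 to one primary region list per task, say whether the PCC is primary, and state which regions form each family.
2. Reconcile the two statements in Section 5.6 on the confirmatory measure. Mean percent signal change, already named under hypothesis testing, is the simplest choice.
3. Replace the fixed 0.02 with a named procedure that holds 5% for that list. Holm needs no correlation input. Hochberg is already in the plan for Aim 3, so it is the smallest change of wording; it relies on the positive correlation that the plan expects. A max-|t| threshold would be about 0.0124 for five regions at 0.54.
4. Restate Aim 1 power for 80 smokers at d=0.36 as about 74% single-step, or under Holm about 72% (one region responding) to 81% (all five). Say that this is for the mean difference, not for the caloric-intake regression.
5. Recheck the Aim 3 power statement that rests on the same 0.02.

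The cost is wording and one standard multiplicity step, with no added participants, visits or scans. Quoted power drops by about 6 points single-step and by up to about 8 points under Holm if only one region responds. There is no loss under Holm if all five respond.

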- Food cue reactivity (fMRI)
- Food reinforcement (fMRI)

Smoking Behavior: Days 1-4* and 29-32

- Self-reported (CO-verified)

Recruitment & Retention Pilot

This pilot study will utilize a randomized controlled trial design to evaluate two components of behavioral economic strategies to improve recruitment and retention. To be eligible for the pilot study participants must meet all eligibility criteria for one of the four participating studies (828958, 824061, 824860, 828125), have a phone capable of receiving SMS messages, and consent to receive SMS messages. ~576 participants will be enrolled across the four participating research studies. All subjects will receive standard text messages and will be randomized to one of four groups (blocked within each study to ensure balanced groups): (1) Standard recruitment (SR): subjects will receive text messages ~2 days prior to their Intake visit with relevant information about the time, date, and location of the visit as well as contact information for study staff ("You have a study visit on [Date] at [Time]. Visit comp is \$10. Reply Y to confirm. See <http://j.mp/2222222> for reminders. Reply or appt may be canceled."); (2) SR + Information Provision (IP): Subjects will receive personalized messages designed to target injunctive norms regarding participating in research (e.g., "[Name], wondering why you should volunteer for research? Many find it a rewarding way to advance science and be a part of a community <http://j.mp/2222222>."); (3) SR + Contingency Management (CM): CM will be provided in the form of an opaque "fishbowl" with a high proportion of chips with little (\$1) monetary value. Participants draw from the fishbowl upon completion of an objectively verified target behavior (e.g., attending an Intake visit), and bonuses are often provided for continued performance [74, 75]. This strategy has been successful in augmenting visit compliance in several treatment studies [80-82]. All text reminders will be delivered using the Way 2 Health (W2H) software platform. Upon completion of all requirements for a given visit, participants will receive 5 fishbowl draws for that visit. Attendance at all visits earns participants bonus draws upon completion of the study. Failure to attend a visit without prior approval or failure to complete all visit requirements results in no draws for that visit. The fishbowl contains 500 chips: 250 say "good job," 219 have a value of \$1, 30 have a value of \$5, and 1 has a value of \$100. The study completion bonus will be 5 extra draws. Thus, at each visit, subjects will have the opportunity to make 5 draws from the fishbowl, for maximum possible earnings of \$120; (4) SR + IP + CM (IC): In this group, subjects will receive the targeted text messages and receive CM.

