
CONFIDENTIAL

This material is the property of the University of Pennsylvania. Do not disclose or use except as authorized in writing by the study sponsor

The design of our study allows us to examine each strategy independently as well as combined to evaluate the optimal approach.

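### Pilot power paragraph: the detectable interaction of 5.5 does not follow from 144 per arm (about 2.75 does), and the claim of more than 80% power holds for the factorial main effects but not for the SR-arm contrast as worded

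*Combined protocol and SAP*

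**What the plan says.** The pilot randomizes about 576 people, who "will be randomized to one of four groups (blocked within each study to ensure balanced groups" (Study Design, Recruitment & Retention Pilot). The arms are standard recruitment (SR), SR plus information provision (IP), SR plus contingency management (CM), and both together, which is a 2x2 factorial layout. Pilot Aim 1 (section 2.2) is "To evaluate the effects of information provision and incentives, alone and in combination, on study enrollment rates", and its hypothesis compares the interventions with standard recruitment. The design section adds that the layout "allows us to examine each strategy independently as well as combined".

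The pilot paragraph in section 5.5 says: "The analysis will compare the enrollment rates between the four intervention arms, and examine main and interaction effects". It expects 28% enrollment in the SR arm and makes two power statements at alpha .05:

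- More than 80% power "to detect a difference between the SR arm and the IP and CM arms of 12%, corresponding to an OR of 1.75".
- For the interaction, 80% power "to detect a departure from additivity of the main effects corresponding to a ratio of odds ratios (ORR) of 5.5".

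The pilot paragraph does not state sidedness. The opening of section 5.5 says of the N=110 sample that it "will achieve at least 80% power using 2-sided tests".

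**The concern.** A ratio of odds ratios of 5.5 is very large for a trial with 144 people per arm and event rates near 30 to 50%, so the figure needed checking. It is also the only sensitivity the plan states for whether the two strategies reinforce or offset each other. Taken at face value, it tells a reader that the pilot can detect only an extreme interaction.

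The main comparison raises a different question. The sentence names a difference between the SR arm and the IP and CM arms. Read literally, the reference group is the 144 people in SR, not the 288 people who make up each side of a factorial main effect. The same 12 points can be well powered or underpowered depending on which is meant, and the paragraph does not say.

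**Working it through.** **Inputs.** Total 576, SR rate 28%, difference 12 points, OR 1.75, alpha .05, power 80% (section 5.5, pilot paragraph); four balanced groups (Study Design), so 576/4 = 144 per arm. Two-sided testing is carried over from the opening of section 5.5 as an assumption. A small point: 28% vs 40% is an OR of (0.40/0.60)/(0.28/0.72) = 1.71, and an OR of 1.75 corresponds to 40.5%.

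**Interaction.** For the log ratio of odds ratios (ROR) in a 2x2 logistic model, SE = sqrt(sum over four cells of 1/(n p(1-p))). Power is 80% when |log ROR| = (1.960 + 0.842) x SE = 2.802 x SE.

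With n = 144 and no main effects, the cells are 28%, 28%, 28% and 51.8%. The sum is 3 x 0.03445 + 0.02781 = 0.1312, so SE = 0.362, log ROR = 1.014 and ROR = 2.76.

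| Main-effect ORs | ROR at 80% power, synergy | ROR at 80% power, antagonism | Power at 5.5 | Power at 1/5.5 | n per arm for 5.5 |
|---|---|---|---|---|---|
| 1, 1 | 2.76 | 1/3.24 | 99.6% | 95.6% | 53 |
| 1.75, 1 | 2.73 | 1/2.88 | 99.5% | 98.6% | 54 |
| 1.75, 1.75 | 2.76 | 1/2.69 | 99.2% | 99.5% | 59 to 60 |

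The last column is n = (2.802/log 5.5)^2 x sum of 1/(p(1-p)). In the top row this is 2.70 x 19.49 = 52.6. For 1/5.5 the requirement is about 54 to 84 per arm.

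Variations in method at 144 per arm do not reach 5.5: null-variance SE gives 2.67 to 2.81, one-sided testing 2.44, alpha .01 gives 3.54, and additivity on the probability scale 2.47. Simulation with 200,000 runs gives 80.0 to 80.3% power at 2.75 and 99.4 to 99.7% at 5.5.

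**Main comparison.** Two-proportion z test with pooled variance under the null: power = Phi((|p2 - p1| - 1.96 x SE0)/SE1).

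- The stated claim reproduces for a factorial main effect, 288 vs 288, 28% vs 40%: SE0 = 0.0395, SE1 = 0.0392, z = 1.09, power 86%.
- SR vs one active arm, 144 vs 144: SE0 = 0.0558, SE1 = 0.0554, z = (0.12 - 0.1094)/0.0554 = 0.19, power 58%.

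| Contrast | 28% vs 40% | OR 1.75 (28% vs 40.5%) |
|---|---|---|
| SR vs IP, or SR vs CM (144 vs 144) | 57.6% | 60.9% |
| SR vs IP and CM pooled (144 vs 288) | 69.4% | 72.8% |
| SR vs all three active arms (144 vs 432) | 74.4% | 77.7% |
| Factorial main effect (288 vs 288) | 86.2% | 88.7% |

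For the pairwise contrast, 80% power needs 28% vs 43.8% (15.8 points, OR about 2.0), or 244 per arm for the stated 12 points.

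The main-effect figure depends on how the combined arm behaves. If effects add on the log-odds scale (28, 40, 40, 53.3%), the margins are 34.0% vs 46.7% and power is 87%. If the combined arm stays at 40%, the margins are 34% vs 40% and power is 32%. The four-arm 3-df test behaves similarly, at 97% and 57%.

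**Do the two statements fit together?** If some unstated loss or variance inflation cut the effective size to the 53 to 59 per arm that 5.5 implies, the 288 vs 288 comparison would become about 106 vs 106 to 118 vs 118, with 45 to 49% power. Even at 84 per arm (168 vs 168) it would be 64%. No single effective sample size makes both sentences true.

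**The case against.** The paragraph says that main and interaction effects will be examined, gives one power statement, and then moves to the interaction as a departure from additivity of the main effects. Read in that order, the 80% sentence is about factorial main effects. On that reading the claim is correct and only loosely worded. This is a fair reading, and the sample size supports it. It does not settle the matter, because the sentence itself names the SR arm and the pilot hypothesis is framed against standard recruitment.

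The 32% figure comes from a strongly antagonistic scenario that the plan does not assume. That is so: it shows what the main-effect power depends on and is not an error in the plan.

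The combination can be tested directly against SR without any interaction. Under additive log-odds (28% vs 53.3%, 144 vs 144) that comparison has about 99% power. This limits the consequences, although the plan states no power for that contrast.

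The models will include a study term and covariates (outcomes section), which the calculation here omits. Such terms are unlikely to double the detectable ratio.

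Sidedness is assumed. One-sided, SR vs IP and CM pooled reaches 79.8% (82.5% at OR 1.75), but the pairwise contrast stays at 69.5% (72.4%).

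Finally, the 5.5 error is conservative and changes no sample size or decision rule. That bears on how serious the error is. The figure still does not follow from its inputs.

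**Conclusion.** The concern holds. From the plan's own inputs the interaction detectable at 80% power is a ratio of odds ratios of 2.73 to 2.76 for synergy, or 1/2.69 to 1/3.24 for antagonism, against 5.5 stated. The plan understates its sensitivity by a factor of about two on the odds-ratio scale.

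The claim of more than 80% power for 12 points is sound for the factorial main effects (about 86%) if there is little interaction. It fails for every two-sided contrast that uses only the SR arm as reference: 58% pairwise, 69% pooled, 74% against all active arms. The wording does not say which is meant.

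These results assume 144 analysed per arm, two-sided alpha .05, no multiplicity adjustment and no covariates. Only the pilot is affected.

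**What to change.** Amend the pilot paragraph of section 5.5 as follows.

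1. Name the contrast to which the 80% refers. If it is the factorial main effects (IP yes/no and CM yes/no, 288 vs 288), say so, give about 86%, and state that this assumes little interaction.
2. Report about 58% power for SR vs IP and SR vs CM at 12 points, with 80% reached at about 16 points (OR about 2.0).
3. Replace 5.5 with about 2.75, stating the assumed main effects and the direction (about 1/2.7 to 1/3.2 for antagonism), or give the assumptions that produce 5.5.
4. State that pilot tests are two-sided, if that is intended.

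The choice of primary contrast is the sponsor's. The cost is protocol wording only, with no added participants. The interaction figure becomes more favourable. If the pairwise contrasts are the intended ones, their figure becomes less so.
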